#### 4.2.3 Data cut offs

There are two planned analyses for this study. The first planned analysis is an interim analysis (IA) when approximately 38 PFS events based on BICR have been observed in the study (25.3% maturity or 76% information fraction). The second planned analysis is the final analysis, which will be conducted when there are approximately 50 BICR-assessed PFS events in total from Arm A and Arm B.

The only data considered post DCO will be the survival update forms completed as part of the survival sweep. Patients who are known to have died or to be alive after the DCO due to the survival sweep will be censored at the DCO. Any other data entered post-DCO will be excluded from the analyses. AEs and medications which started before the DCO but finished after the DCO will be reported in the analysis as ongoing and the end date will be reported as missing.

#### 4.2.4 General considerations for safety and CCI

Time windows will be defined for any presentations that summarize values by visit. The following conventions will apply:

- The time windows will be exhaustive so that data recorded at any time point has the potential to be summarized. Inclusion within the time window will be based on the actual date and not the intended date of the visit.
- All unscheduled visit data have the potential to be included in the summaries.
- The window for the visits following baseline will be constructed in such a way that the upper limit of the interval falls half way between the two visits (the lower limit of the first post-baseline visit will be Day 2). If an even number of days exists between two consecutive visits, then the upper limit will be taken as the midpoint value minus 1 day. For example, the visit windows for vital signs data are:

- Day 8, visit window 2 – 11
  - Day 15, visit window 12 – 18
  - Day 22, visit window 19 – 25
  - Day 29, visit window 26 – 32
  - Day 36, visit window 33 – 39
  - Day 43, visit window 40 – 46
- 
- For summaries showing the maximum or minimum values, the maximum/minimum value recorded on treatment will be used (regardless of where it falls in an interval).
  - Listings should display all values contributing to a time point for a patient.
  - For visit-based summaries
    - If there is more than one value per patient within a time window then the closest value to the scheduled visit date will be summarized, or the earlier, in the event the values are equidistant from the nominal visit date. The listings will highlight the value for the patient that contributed to the summary table, wherever feasible. Note: in summaries of extreme values all post baseline values collected are used including those collected at unscheduled visits regardless of whether or not the value is closest to the scheduled visit date
  - For summaries at a patient level, all values will be included, regardless of whether they appear in a corresponding visit-based summary, when deriving a patient level statistic such as a maximum.
  - For summaries showing shift from baseline (e.g. NCI CTCAE grades) all values will be included, regardless of whether they appear in a corresponding visit-based summary.

Missing safety data will generally not be imputed. However, safety assessment values of the form of “< x” (i.e. below the lower limit of quantification) or > x (i.e. above the upper limit of quantification) will be imputed as “x” in the calculation of summary statistics but displayed as “< x” or “> x” in the listings. Additionally, adverse events that have missing causality (after data querying) will be assumed to be related to study drug.

Furthermore:

- For missing diagnostic dates, if day and/or month are missing use 01 and/or Jan. If year is missing, put the complete date to missing.
- For missing AE and medication/radiotherapy start dates, the following will be applied
  - a. Missing day- Impute the 1st of the month unless month is the same as month of the first dose of study drug then impute first dose date
  - b. Missing day and month -Impute 1st January unless year is the same as first dose date then impute first dose date

- c. Completely missing-impute first dose date unless the end date suggests it could have started prior to this in which case impute the 1st January of the same year as the end date
- For missing AE and medication/radiotherapy end dates, the following will be applied:
  - a. Missing day - Impute the last day of the month
  - b. Missing day and month – impute 31st December. Flags will be retained in the database indicating where any programmatic imputation has been applied, and in such cases, any durations would not be calculated.

#### 4.2.5

CCI

#### 4.2.5.1

CCI

#### 4.2.5.2

CCI

#### 4.2.5.3

CCI

#### 4.2.6 Safety

All safety summaries will use the safety analysis set. Safety analyses, except for death, will include data only prior to crossover for patients from Arm B. Selected outputs will be repeated for the crossover period.

#### 4.2.6.1 Exposure

Summary statistics will be calculated for total exposure, actual exposure and RDI for each study drug. Additionally, a categorical summary of RDI will be produced, with categories < 80%, 80 – 120% and > 120%.

For patients who received acalabrutinib monotherapy, dose withholding and dose reduction will be summarized along with the reasons. For patients who received rituximab, dose delay and infusion interruption will be summarized along with the reasons. For patients who received Chlorambucil, dose interruption (defined as skip one or more dose in one cycle), dose delay and dose reduction will be summarized along with the reasons. Acalabrutinib dose reduction is defined as taking lower dose level (100 mg QD) for  $\geq 3$  consecutive days, dose withholding is defined as missing dose for  $\geq 7$  consecutive days.

Total exposure, actual exposure, RDI and dose modifications will also be analyzed for the crossover period.

#### 4.2.6.2 Adverse events (AEs)

All TEAEs, both in terms of current MedDRA preferred term and NCI CTCAE grade, will be summarized descriptively by count (n) and percentage (%) for each treatment group. The current MedDRA dictionary will be used for coding.

An overall summary of the number and percentage of patients in each of the following categories will be presented:

- All treatment emergent adverse events (AEs)
- All related AEs
- AEs with outcome of death
- Related AEs with outcome of death
- Serious AEs (SAEs)
- Related SAEs
- AEs leading to discontinuation of IP
- Related AEs leading to discontinuation of IP
- AEs leading to IP dose interruptions/delays\*
- Related AEs leading to IP dose interruptions/delays\*
- AEs leading to IP dose reduction

- Related AEs leading to IP dose reduction

\*AE leading to dose delay only applies to Arm B.

The overall summary will be repeated for the crossover period.

All AEs will be listed, including AEs which are reported more than 30 days after last dose. AEs which occur after the first dose of crossover therapy will be flagged in the listings as well as AEs which occur after the initiation of any other subsequent therapies.

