4.2 Scientific rationale for study design

This is a Phase 3, randomized, controlled study to assess the benefit/risk profile of acalabrutinib monotherapy versus rituximab in combination with chlorambucil. Given the different treatment administration schedules and treatment durations, this study will use an open-label design.

This study is targeting the medically unfit CLL subjects, and rituximab in combination with chlorambucil was selected as the comparator per Chinese CLL/SLL Diagnostic and Treatment Guideline ([Version 2018](#)) as one of the preferred regimens. NCCN Guidelines ([Version 5 2019](#)) also recommend chlorambucil plus anti-CD20 monoclonal antibody for frail patients with significant comorbidity (not able to tolerate purine analogs), patients aged ≥ 65 years, and younger patients with significant comorbidities. Currently, rituximab is the only NCCN-recommended anti-CD20 antibody approved in China.

For CLL patients who are elderly and/or have comorbidities that make them ineligible for fludarabine-based treatment, chlorambucil plus rituximab is an appropriate therapeutic option. In the Phase 2 National Cancer Research Institute Study CLL208, a total of 100 patients were treated with rituximab-chlorambucil, with a median follow-up of 30 months ([Hillmen G et al. 2014](#)). Median age of patients was 70 years (range 43 to 86 years), with patients having a median of 7 comorbidities. Overall response rates in the CLL208 study were 84%, with CR achieved in 10% of patients. Median PFS was 23.5 months. Hematologic toxicities accounted for most Grade 3-4 AEs reported, with neutropenia and lymphopenia both occurring in 41% of patients and leukopenia occurring in 23% of patients.

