6.1.2 Chlorambucil and Rituximab

Rituximab will be administered as described in Table 6, on Days of Cycles 1 through 6.

Locally approved labelling may be considered for administration of rituximab.

Chlorambucil will be orally administered at a dose of 0.5 mg/kg of body weight on Days 1 and 15 of Cycles 1 through 6. Chlorambucil should not be dosed sooner than 14 days from the last dose of chlorambucil. On days when chlorambucil and rituximab are both administered, the order of study treatment administration will be chlorambucil followed by rituximab.

The subject's body weight at screening and body surface area (BSA) calculated at screening should be used to calculate the dose of chlorambucil, rituximab throughout the study unless the subject's weight increases or decreases by $\geq 10\%$ from screening.

Table 6 Study Treatments

	Arm A	Arm B	
Study treatment name:	Acalabrutinib (ACP-196)	Chlorambucil	Rituximab
Dosage formulation:	100 mg capsule for oral administration	As sourced locally	10 mL (100 mg) and 50 mL (500 mg) vial solution for infusion after dilution, 10 mg/mL
Route of administration:	Oral	Oral	IV infusion

Table 6 Study Treatments

	Arm A	Arm B	
Dosing instructions:	One Capsule of 100 mg twice daily orally with approximately 240 mL of water. It may be taken with or without food. The capsule should be swallowed intact and should not be opened or dissolved in liquid. Doses should be administered approximately 12 hours apart (recommended to be taken as close as the schedule time as possible preferably within ± 1 hour). If a dose is missed, it can be taken up to 3 hours after the scheduled time with a return to the normal schedule with the following dose. If it has been >3 hours, the dose should not be taken. The missed dose will not be made up and must be returned to the site at the next schedule time.	0.5 mg/kg body weight orally on Day 1 and Day 15 of all treatment cycles (Cycles 1-6) Chlorambucil should not be dosed sooner than 14 days from the last dose of chlorambucil. On days when chlorambucil and rituximab are both administered, the order of study treatment administration will be chlorambucil followed by rituximab.	375 mg/m ² of rituximab IV infusion on Day 1 of the first treatment cycle (Cycle 1). ^a 500 mg/m ² IV infusion on Day 1 for each of subsequent cycles (Cycles 2-6). Premedicate before each infusion with acetaminophen and an antihistamine in accordance with local prescribing information.

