6.6.2 Rituximab and chlorambucil

If a patient experiences any \geq Grade 2 non-hematological toxicity, chlorambucil and/or rituximab should be hold until the non-hematological toxicity returns to Grade 1 or baseline. If treatment is delayed for more than 4 weeks due to study drug-related toxicity, chlorambucil and/or rituximab should be discontinued.

If a patient experiences Grade 3 or 4 cytopenia, the guidelines for dose delay (chlorambucil or rituximab) and dose reduction (chlorambucil only) are outlined in [Table 9](#).

Table 9 Rituximab and Chlorambucil Dose Modification

	Chlorambucil	Rituximab
Grade 3 or 4 cytopenia	Delay dosing for a maximum of 4 weeks. Administer G-CSF for neutropenia or platelets or red blood cells as required. 1st episode : If improvement to Grade ≤ 2 (or baseline), decrease Clb dose to 75% of initial dose for subsequent cycles 2nd episode : If improvement to Grade ≤ 2 (or baseline), decrease Clb dose to 50% of initial dose for subsequent cycles 3rd episode : Discontinue Clb	If improvement to Grade ≤ 2 (or baseline), administer full dose. If Clb is discontinued, rituximab may continue at the investigator's discretion.
Grade 1 or 2 cytopenia	No dose reduction or delay	No dose reduction or delay
Abbreviations: Clb=chlorambucil; G-CSF=granulocyte colony-stimulating factor.		

No reduction in the dose of rituximab is allowed. Severe, including fatal, infusion reactions can occur with rituximab. Discontinue rituximab infusion and provide medical treatment for Grade 3 or 4 infusion reactions. For less severe infusion reactions (grade 1 or 2), interrupt the infusion or slow the infusion rate. Rituximab may continue at the discretion of the investigator when the toxicity has improved (Grade ≤ 2 for hematological toxicity and Grade 1 or baseline for non-hematological toxicity). If rituximab is discontinued, the patient is

withdrawn from study treatment. Refer to the rituximab local prescribing information for dose withholding or discontinuation in response to specific toxicities associated with rituximab.

Chlorambucil dose reductions are described in Table 9. Once reduced, the dose of chlorambucil should not be escalated. A delay of up to 4 weeks is permitted for chlorambucil to allow recovery of hematologic toxicities to Grade ≤ 2 or non-hematologic toxicities to Grade 1 or baseline level. If the treatment is delayed for more than 4 weeks due to toxicity, chlorambucil should be discontinued.

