If a Grade 3 or 4 cytopenia prevents treatment on Day 15 (of any cycle for Arm B), the Day 15 chlorambucil dose will be skipped in order to keep the antibody on schedule. Rituximab + chlorambucil administration on Day 1 of the following cycle will be given if the cytopenia has resolved to Grade ≤ 2 . Chlorambucil will be given at a reduced dose. If the cytopenia persists, rituximab + chlorambucil administration will be delayed until the cytopenia has improved to Grade ≤ 2 .

Chlorambucil has been reported to exacerbate or precipitate autoimmune hemolytic anemia and patients should be monitored carefully for this condition. If a rapid decrease of hemoglobin occurs during therapy, the possibility of chlorambucil- or autoantibody-induced hemolysis should be considered and appropriate diagnostic tests (LDH, bilirubin, haptoglobin, reticulocytes, Coombs test) should be performed. If hemolysis is suspected, a Coombs test should be performed. If, in the judgment of the treating physician, there is evidence of clinically significant hemolytic anemia secondary to chlorambucil, study treatment should be promptly withdrawn. Full details of the hemolytic anemia should be recorded on the adverse event pages of the eCRF.

As many of these patients have multiple comorbidities, treatment may be delayed longer than 4 weeks (for both treatments) to enable resolution of unrelated AEs, concurrent diseases, or recovery from surgical procedures. This is at the investigators discretion but should be discussed in advance with the sponsor.

A patient should discontinue study treatment with chlorambucil/rituximab if any of the following occur:

- Grade 4 infusion related symptom (patient should be withdrawn immediately)
- Grade 3 infusion related symptom at re-challenge
- Grade 3 or 4 cytopenia that has not resolved to Grade ≤ 2 and delays treatment by 4 weeks
- Grade ≥ 2 non-cytopenic toxicity that does not resolve to Grade 1/baseline and delays treatment by 4 weeks

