## 1.2 Study Design

This randomized, regional, multicenter, open-label, Phase 3 study will evaluate the efficacy and safety of acalabrutinib monotherapy (Arm A) versus chlorambucil plus rituximab (Arm B) in patients with previously untreated Chronic Lymphocytic Leukemia (CLL) without del(17p) or TP53 mutation.

[figure not shown]
Study assessments will be conducted in accordance with the schedule of assessments, which can be found in the CSP, section 1.1. See Figure 1 below for a graphical representation of the study design.

Patient participation will include a screening phase, treatment phase, post-treatment disease follow-up phase, and survival follow-up phase. The screening phase will last up to 28 days before the first dose of study drug, during which the patient's eligibility and baseline characteristics will be determined. The treatment phase will last from randomization until study drug(s) discontinuation for the purpose of efficacy analyses, and from first dose to study drug(s) discontinuation for safety analyses. Treatment with acalabrutinib may be continued until disease progression or any other treatment discontinuation criterion is met. Treatment with chlorambucil/rituximab includes maximum 6 cycles, or until there is disease progression or any other treatment discontinuation criterion is met. In both treatment arms a cycle is defined as 28 days ( $\pm 3$  days for Arm B).

Patients randomized to Arm B who have blinded independent central review (BICR) confirmed disease progression may be eligible to crossover and receive single agent acalabrutinib 100 mg BID at investigator discretion provided they meet the crossover eligibility criteria, as defined in the CSP. An end of treatment (EoT) visit is required for safety assessments for any patients who permanently discontinue study drug for any reason (except for death, lost to follow-up, or withdrawal of consent), including disease progression. The EoT visit should be performed within 7 days of the last dose of all study drugs, if possible, and is not required for patients who discontinue from study drug within 10 days of a scheduled study visit, or if the EoT visit would be performed within 14 days of the safety follow-up (SFU) visit.

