### 3.5.2 Adverse events

AEs will be collected throughout the study, from date of informed consent until 30 days after the last dose of study drug. SAEs will be collected from the date of informed consent. The following events will be considered treatment emergent:

- Adverse events with an onset date on or after first dose of study drug, and within 30 days after last dose of study drug or the initiation of a subsequent therapy (including crossover treatment), whichever occurs first.
- Worsening of pre-existing events on or after first dose of study drug, and within 30 days after last dose of study drug or the initiation of a subsequent therapy (including crossover treatment), whichever occurs first.

The Medical Dictionary for Regulatory Activities (MedDRA) (using the latest or current MedDRA version) will be used to code the AEs. AEs will be graded according to the

National Cancer Institute Common Terminology Criteria for AEs (using the NCI CTCAE version 5.0).

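### Adverse events are tabulated side by side as crude percentages although the Arm B window closes near day 185 and the Arm A window is open-ended; add a common-period table, with patient-year rates second

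*SAP*

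**What the plan says.** SAP 4.2.6.2 states that treatment-emergent AEs "will be summarized descriptively by count (n) and percentage (%) for each treatment group". The overview, the system organ class and preferred term tables, and the Grade ≥3, SAE and event-of-clinical-interest (ECI) tables follow the same patient-count approach.

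SAP 3.5.2 counts an event as treatment-emergent if it starts on or after first dose and "within 30 days after last dose of study drug or the initiation of a subsequent therapy (including crossover treatment), whichever occurs first".

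Treatment length differs by design. SAP 1.2 says of Arm B: "Treatment with chlorambucil/rituximab includes maximum 6 cycles", in 28-day cycles, and Protocol 6.1.2 places chlorambucil "on Days 1 and 15 of Cycles 1 through 6". Of Arm A, SAP 1.2 says: "Treatment with acalabrutinib may be continued until disease progression or any other treatment discontinuation criterion is met".

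The Arm B course can stretch. Protocol 6.6.2 has, for Grade 3 or 4 cytopenia, "Delay dosing for a maximum of 4 weeks", and says elsewhere that "treatment may be delayed longer than 4 weeks (for both treatments) to enable resolution of unrelated AEs".

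The safety objective (Protocol Table 4, SAP Table 1) is worded as a comparison of acalabrutinib with chlorambucil plus rituximab. The Protocol synopsis makes safety descriptive, without formal analysis.

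**The concern.** A percentage of patients with at least one event depends on how often events occur and on how long patients are observed. Here observation differs by arm because of the design. A reader comparing the two columns cannot tell a higher event rate from a longer window.

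With equal hazards that persist over time, the crude table errs against acalabrutinib. The distortion is largest for uncommon events that accrue steadily. Protocol 2.3.1.1 lists infection, hemorrhage, second primary malignancy and atrial fibrillation as important identified risks; if these accrue over time, they would be affected.

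Extending Arm B observation cannot close the gap. Under Protocol 8.3.1, after 30 days from last dose only related SAEs and AEs of concern are reported.

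**Working it through.** The documents state no length for either arm's AE window, so there is no figure of theirs to reproduce.

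**1. Arm B completer, no delay.** Last planned chlorambucil is Cycle 6 Day 15: 5 × 28 + 15 = day 155. Adding 30 days closes the window on day 185 (6.1 months). Stopping after the Day 15 dose of Cycle 3 would close it on day 2 × 28 + 15 + 30 = 101. One 28-day delay would move a completer's closing day to 213.

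**2. Arm A window.** W = min(T + 30 days, F).
- F is follow-up to data cut-off. Accrual is 30 months (Protocol 9.2) and the final analysis was about 45 months after first randomization (Protocol 4.4), so F runs from 15 to 45 months. Uniform accrual is an assumption.
- T is time to stopping, taken as exponential with daily hazard h. It combines the planned 90-month median PFS with an assumed fraction d a year stopping for other reasons: h = [ln 2/90 − ln(1 − d)/12]/30.44.
- For given F, mean W = 30 + [1 − exp(−h(F − 30))]/h, with F in days.

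For d = 0, h = 0.000253 a day. At F = 30 months (913 days), W = 30 + [1 − exp(−0.2235)]/0.000253 ≈ 821 days. Averaging over F from 15 to 45 months gives 814 days, and 814/185 = 4.4.

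Mean Arm A window in days (ratio to 185), by cut-off and d. The 40- and 53-month rows are the planned interim and final times in Protocol 9.2:

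| Cut-off | d = 0% | 10% | 20% | 30% |
|---|---|---|---|---|
| 40 months | 690 (3.7) | 621 (3.4) | 556 (3.0) | 494 (2.7) |
| 45 months | 814 (4.4) | 720 (3.9) | 634 (3.4) | 554 (3.0) |
| 53 months | 1004 (5.4) | 863 (4.7) | 739 (4.0) | 629 (3.4) |

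Against an Arm B course with one 28-day delay (213 days), the 45-month ratios are 814/213 = 3.8 down to 554/213 = 2.6.

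**3. Effect on crude percentages.** Give both arms the same hazard. If a fraction p of Arm B completers has an event by day 185, λ = −ln(1 − p)/185. For p = 5%, λ = 0.0513/185 = 0.000277 a day. The Arm A percentage is the mean of 1 − exp(−cumulative hazard over W). At the 45-month cut-off, for d from 0% to 30%:

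| Arm B | Arm A, constant hazard | Arm A, hazard halved after day 185 | Arm A, no hazard after day 185 |
|---|---|---|---|
| 5% | 20–14% | 13–9% | about 5% |
| 10% | 36–26% | 24–18% | 10–9% |
| 23% | 65–49% | 49–38% | 23–21% |
| 41% | 85–69% | 73–60% | 40–38% |

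The 23% and 41% rows borrow the rituximab-chlorambucil figures in Protocol 4.2 ("with neutropenia and lymphopenia both occurring in 41% of patients and leukopenia occurring in 23% of patients"), which stand in that section's sentence on Grade 3–4 AEs. They are arithmetic illustrations only. No row predicts acalabrutinib AE rates.

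**4. How the two possible remedies behave under identical hazards** (45-month cut-off, Arm B incidence 5–41%, d from 0% to 30%):

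| Hazard after day 185 | Percentage ratio A/B, onset limited to 185 days | Patient-year rate ratio A/B |
|---|---|---|
| unchanged | 0.93–0.99 | 1.00 |
| halved | 0.93–0.99 | 0.62–0.74 |
| zero | 0.93–0.99 | 0.23–0.37 |

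The common-period ratio falls slightly below 1 because some Arm A patients stop before day 185 while the modelled Arm B patient is a completer. The patient-year rate spreads early events over Arm A's longer exposure and so favours acalabrutinib when events cluster early.

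**The case against.** The case for leaving the plan alone has substance. Nothing confirmatory depends on these tables. SAP 4.2.6.2 summarizes and does not test. With equal hazards that persist, the crude table errs against the sponsor's drug.

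The plan also gives partial help:
- exposure by drug (SAP 4.2.6.1);
- event counts where appropriate, and separate presentation of pre-treatment, treatment-emergent and post-treatment AEs (Protocol 9.5.2);
- by-visit laboratory, vital-sign and ECOG summaries (SAP 4.2.6.3 to 4.2.6.5);
- a full AE listing (SAP 4.2.6.2).

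The study is already unblinded, so nothing added now is prespecified. All of this stands, and it keeps the point at the level of an improvement. It does not close the gap. Event counts carry no time at risk, the by-visit summaries do not cover AEs, routine collection stops 30 days after last dose, and a listing leaves the calculation to the reader.

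Stronger readings are tempting but unsupported. A reader might infer that acalabrutinib will look three or four times as toxic. That needs an equal, constant hazard and an uncommon event, and the documents give neither hazards nor an acalabrutinib stopping rate. A reader might infer that patient-year rates should replace the percentages; step 4 shows that they can introduce the opposite bias. Nor is there a between-arm distortion in AESIs, because both documents define these for acalabrutinib subjects only. Finally, day 185 is not a fixed limit for Arm B: early stopping shortens the window and permitted delays lengthen it.

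**Conclusion.** The point holds as a low-cost, optional improvement. It is not an error in a test or in a stated figure. The planned AE percentages mix event rate with window length, and no readable passage provides a summary that separates them; removed or redacted text could not be checked.

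The mean Arm A window is about 3.0–4.4 times the Arm B completer window at the 45-month cut-off, and 2.7–5.4 times over cut-offs of 40–53 months. This rests on the planned 90-month median PFS, exponential times, uniform accrual and non-progression stopping of 0–30% a year. The last two are not in the documents, and the model ignores closure of the Arm A window by early subsequent therapy. The distortion of a given percentage depends on how common the event is and when it occurs: large for uncommon events spread over time, absent for events confined to the first six months.

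**What to change.** Keep every planned n (%) table and footnote that the treatment-emergent windows differ in length between arms. Add two outputs, labelled supplementary because the study is unblinded:

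1. **Lead output:** an AE overview (TEAEs, Grade ≥3 AEs, SAEs, each ECI) limited to onset in the first 185 days from first dose in both arms, reporting how many Arm B patients were still in their treatment-emergent window after day 185.
2. **Secondary output:** first-event incidence per 100 patient-years at risk within the treatment-emergent window, by arm, for the same categories.

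The cost is a few post hoc tables from data already collected. State the limits beside them. Output 1 is nearly unbiased under equal hazards, but says nothing about late events and omits those in delayed Arm B courses: with one 28-day delay, 28 of 213 days (13%) of the window fall after day 185. Output 2 assumes a roughly constant hazard and favours acalabrutinib when events cluster early, so it must not be presented alone.
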